Note: Missing values are imputed using LOCF.

SOURCE: USERNAME\SPONSOR\PROJECT\JOBNAME (DATE,TIME)

Repeat Table 14.2.3.6.1 for the following:

Table 14.2.3.6.2: Summary of Investigator Global Assessment by Visit (mITT Population)

Table 14.2.3.6.3: Summary of Investigator Global Assessment by Visit (PP Population)

**Programming note:** *Replace footnote with* - Note: No imputations were made for missing data.

Table 14.2.3.7.1: Exploratory Endpoint: Change from Baseline in Signs of AD Total Score at Target Lesions at Days 29, 57 and 85  
(ITT Population)  
(Page 1 of 2)

	BTX 1204 4% BID (N=xxx)	Vehicle BID (N=xxx)	Treatment P-Value
Change from Baseline in Total Signs of AD			
Day 29			
n	xx	xx	
Mean	xx.x	xx.x	
SD	xx.xx	xx.xx	
Median	xx.x	xx.x	
Min., Max.	xx, xx	xx, xx	
LSMean a	xx.x		x.xxx a
LSSD a	xx.xx		
Day 57			
n	xx	xx	
Mean	xx.x	xx.x	
SD	xx.xx	xx.xx	
Median	xx.x	xx.x	
Min., Max.	xx, xx	xx, xx	
LSMean a	xx.x		x.xxx a
LSSD a	xx.xx		

a Least squares mean, standard deviation, and p-value from an analysis of covariance with baseline Total Signs of AD and treatment as covariates.

Note: Missing values imputed using LOCF.

SOURCE: USERNAME\SPONSOR\PROJECT\JOBNAME (DATE, TIME)

Table 14.2.3.7.1: Exploratory Endpoint: Change from Baseline in Signs of AD Total Score at Target Lesions at Days 29, 57 and 85  
(ITT Population)  
(Page 2 of 2)

	BTX 1204 4% BID (N=xxx)	Vehicle BID (N=xxx)	Treatment P-Value
Change from Baseline in Total Signs of AD			
Day 29			
n	xx	xx	
Mean	xx.x	xx.x	
SD	xx.xx	xx.xx	
Median	xx.x	xx.x	
Min., Max.	xx, xx	xx, xx	
LSMean a	xx.x		x.xxx a
LSSD a	xx.xx		

a Least squares mean, standard deviation, and p-value from an analysis of covariance with baseline Total Signs of AD and treatment as covariates.

Note: Missing values imputed using LOCF.

SOURCE: USERNAME\SPONSOR\PROJECT\JOBNAME (DATE, TIME)

Repeat Table 14.2.3.7.1 for the following:

Table 14.2.3.7.2: Exploratory Endpoint: Change from Baseline in Signs of AD Total Score at Target Lesions at Days 29, 57 and 85 (mITT Population)

Table 14.2.3.7.3: Exploratory Endpoint: Change from Baseline in Signs of AD Total Score at Target Lesions at Days 29, 57 and 85 (PP Population)

**Programming note:** *Replace footnote with* - Note: No imputations were made for missing data.

Table 14.2.3.8.1: Exploratory Efficacy Endpoint: Summary of Signs of AD Score at Target Lesions by Visit  
(ITT Population)  
(Page 1 of x)

	BTX 1204 4% BID (N=xxx)	Vehicle BID (N=xxx)
Erythema		
Baseline		
n	xx	xx
Mean	xx.x	xx.x
SD	xx.xx	xx.xx
Median	xx.x	xx.x
Min., Max.	xx, xx	xx, xx
Day 15		
n	xx	xx
Mean	xx.x	xx.x
SD	xx.xx	xx.xx
Median	xx.x	xx.x
Min., Max.	xx, xx	xx, xx
Change from Baseline		
n	xx	xx
Mean	xx.x	xx.x
SD	xx.xx	xx.xx
Median	xx.x	xx.x
Min., Max.	xx, xx	xx, xx

Note: Missing values are imputed using LOCF.

SOURCE: USERNAME/SPONSOR/PROJECT/JOBNAME (DATE,TIME)

Table 14.2.3.8.1: Exploratory Efficacy Endpoint: Summary of Signs of AD Score at Target Lesions by Visit  
(ITT Population)  
(Page 2 of x)

	BTX 1204 4% BID (N=xxx)	Vehicle BID (N=xxx)
Erythema		
Day 29		
n	xx	xx
Mean	xx.x	xx.x
SD	xx.xx	xx.xx
Median	xx.x	xx.x
Min., Max.	xx, xx	xx, xx
Change from Baseline		
n	xx	xx
Mean	xx.x	xx.x
SD	xx.xx	xx.xx
Median	xx.x	xx.x
Min., Max.	xx, xx	xx, xx
Day 57		
n	xx	xx
Mean	xx.x	xx.x
SD	xx.xx	xx.xx
Median	xx.x	xx.x
Min., Max.	xx, xx	xx, xx
Change from Baseline		
n	xx	xx
Mean	xx.x	xx.x
SD	xx.xx	xx.xx
Median	xx.x	xx.x
Min., Max.	xx, xx	xx, xx

Note: Missing values are imputed using LOCF.

SOURCE: USERNAME\SPONSOR\PROJECT\JOBNAME (DATE,TIME)

**Programming note:** Continue for Exudation, Excoriation, Induration/Papulation, Lichenification, and Total Score

Repeat Table 14.2.3.8.1 for the following:

Table 14.2.3.8.2: Exploratory Efficacy Endpoint: Summary of Signs of AD Score at Target Lesions by Visit (mITT Population)

Table 14.2.3.8.3: Exploratory Efficacy Endpoint: Summary of Signs of AD Score at Target Lesions by Visit (PP Population)

**Programming note:** *Replace footnote with* - Note: No imputations were made for missing data.

Table 14.3.0.1: Summary of Extent of Exposure  
(Safety Population)  
(Page 1 of 2)

	BTX 1204 4% BID (N=xxx)	Vehicle BID (N=xxx)
Total Amount of Study Drug Used (g)		
n	xx	xx
Mean	xx.x	xx.x
SD	xx.xx	xx.xx
Median	xx.x	xx.x
Min., Max.	xx, xx	xx, xx
Number of Applications		
n	xx	xx
Mean	xx.x	xx.x
SD	xx.xx	xx.xx
Median	xx.x	xx.x
Min., Max.	xx, xx	xx, xx
Number of Missed Applications		
n	xx	xx
Mean	xx.x	xx.x
SD	xx.xx	xx.xx
Median	xx.x	xx.x
Min., Max.	xx, xx	xx, xx

a Compliant with the dosing regimen is if the subject applied at least 80% but no more than 120% of expected applications while enrolled in the study.

b Percentages based on the number of subject in the safety population with percent compliance calculated.

SOURCE: USERNAME/SPONSOR/PROJECT/JOBNAME (DATE,TIME)

Table 14.3.0.1: Summary of Extent of Exposure  
(Safety Population)  
(Page 2 of 2)

	BTX 1204 4% BID (N=xxx)	Vehicle BID (N=xxx)
Percent Compliance		
n	xx	xx
Mean	xx.x	xx.x
SD	xx.xx	xx.xx
Median	xx.x	xx.x
Min., Max.	xx, xx	xx, xx
Compliant a		
Yes b	xx ( xx.x%)	xx ( xx.x%)
No b	xx ( xx.x%)	xx ( xx.x%)

a Compliant with the dosing regimen is if the subject applied at least 80% but no more than 120% of expected applications while enrolled in the study.

b Percentages based on the number of subject in the safety population with percent compliance calculated.

SOURCE: USERNAME\SPONSOR\PROJECT\JOBNAME (DATE,TIME)

Table 14.3.1.1: Summary of Treatment-Emergent Adverse Event Characteristics  
(Safety Population)

	BTX 1204 4% BID (N=xxx)	Vehicle BID (N=xxx)
Number (%) of Subjects Reporting At Least One Treatment-Emergent Adverse Event	xx ( xx.x%)	xx ( xx.x%)
Number of Treatment-Emergent Adverse Events	xx	xx
Number (%) of Subjects Reporting At Least Once Serious Treatment-Emergent Adverse Event	xx ( xx.x%)	xx ( xx.x%)
Number of Serious Treatment-Emergent Adverse Events	xx	xx
Number (%) of Subjects who Discontinued Study Due to At Least One Treatment-Emergent Adverse Event	xx ( xx.x%)	xx ( xx.x%)
Number of Treatment-Emergent Adverse Events Leading to Discontinuation of Study	xx	xx
Maximum Severity		
Severe	xx ( xx.x%)	xx ( xx.x%)
Moderate	xx ( xx.x%)	xx ( xx.x%)
Mild	xx ( xx.x%)	xx ( xx.x%)
Strongest Relationship to Study Drug		
Related	xx ( xx.x%)	xx ( xx.x%)
Not Related	xx ( xx.x%)	xx ( xx.x%)

Note: Treatment-emergent adverse events are those with an onset on or after the date of first application of study drug.

Percentages are based on the number of subjects in each treatment group in the Safety population.

Related adverse events include possibly, probably, and definitely responses to relationship to study drug question.

SOURCE: USERNAME\SPONSOR\PROJECT\JOBNAME (DATE,TIME)

Table 14.3.1.2: Summary of Treatment-Emergent Adverse Event by MedDRA System Organ Class and Preferred Term (Safety Population)

System Organ Class a Preferred Term	BTX 1204 4% BID (N=xxx)	Vehicle BID (N=xxx)
System Organ Class 1	xx ( xx.x%)	xx ( xx.x%)
Preferred Term 1	xx ( xx.x%)	xx ( xx.x%)
Preferred Term 2	xx ( xx.x%)	xx ( xx.x%)
...	xx ( xx.x%)	xx ( xx.x%)
Preferred Term x	xx ( xx.x%)	xx ( xx.x%)
...	xx ( xx.x%)	xx ( xx.x%)

xx ( xx.x%)

a At each level of summarization (System Organ Class or Preferred Term) subjects are counted once.  
Note: MedDRA Version xx.x.

Treatment-emergent adverse events are those with an onset on or after the date of first application of study drug.

Percentages are based on the number of subjects in each treatment group in the Safety population.

SOURCE: USERNAME\SPONSOR\PROJECT\JOBNAME (DATE,TIME)

Repeat Table 14.3.1.2 for the following:

Table 14.3.1.3: Summary of Serious Treatment-Emergent Adverse Events by MedDRA System Organ Class and Preferred Term (Safety Population)

Table 14.3.1.4: Summary of Related Treatment-Emergent Adverse Events by MedDRA System Organ Class and Preferred Term (Safety Population)  
**Programming note:** *Add footnote* - Related adverse events include possibly, probably, and definitely responses to relationship to study drug question.

Table 14.3.1.5: Summary of Severe Treatment-Emergent Adverse Events by MedDRA System Organ Class and Preferred Term (Safety Population)

Table 14.3.1.6: Summary of Treatment-Emergent Adverse Events Leading to Study Discontinuation by MedDRA System Organ Class and Preferred Term (Safety Population)

Table 14.3.1.7: Summary of Time to Study Discontinuation for Subjects Who Discontinue Due to Treatment-Emergent Adverse Events  
(ITT Population)

	BTX 1204 4% BID (N=xxx)	Vehicle BID (N=xxx)
Time to Study Discontinuation a		
n	xx	xx
Mean	xx.x	xx.x
SD	xx.xx	xx.xx
Median	xx.x	xx.x
Min., Max.	xx, xx	xx, xx

a Time to Study Discontinuation is calculated as study discontinuation date – date of first dose.  
SOURCE: USERNAME\SPONSOR\PROJECT\JOBNAME (DATE,TIME)

Repeat Table 14.3.1.2 for the following:

Table 14.3.1.8: Summary of Treatment-Emergent Abuse-Related Adverse Events by MedDRA System Organ Class and Preferred Term (Safety Population)

Table 14.3.2.1.1: Summary of Chemistry Results by Visit  
(Safety Population)  
(Page 1 of y)

Test Name (Units)	BTX 1204 4% BID (N=xxx)	Vehicle BID (N=xxx)
Baseline		
n	xx	xx
Mean	xx.x	xx.x
SD	xx.xx	xx.xx
Median	xx.x	xx.x
Min., Max.	xx, xx	xx, xx
Day 85		
n	xx	xx
Mean	xx.x	xx.x
SD	xx.xx	xx.xx
Median	xx.x	xx.x
Min., Max.	xx, xx	xx, xx
Change from Baseline		
n	xx	xx
Mean	xx.x	xx.x
SD	xx.xx	xx.xx
Median	xx.x	xx.x
Min., Max.	xx, xx	xx, xx

[repeat for each test]

SOURCE: USERNAME\SPONSOR\PROJECT\JOBNAME (DATE,TIME)

Table 14.3.2.1.2: Shift Table for Chemistry Results  
(Safety Population)  
(Page 1 of y)

Test Name (Units)	Day 85 (Na=xx)	Baseline		
		BNL	WNL	ANL
BTX 1204 4% BID (N=xx)	BNL	xx ( xx.x%)	xx ( xx.x%)	xx ( xx.x%)
	WNL	xx ( xx.x%)	xx ( xx.x%)	xx ( xx.x%)
	ANL	xx ( xx.x%)	xx ( xx.x%)	xx ( xx.x%)
Vehicle BID (N=xx)	Day 85 (Na=xx)			
	BNL	xx ( xx.x%)	xx ( xx.x%)	xx ( xx.x%)
	WNL	xx ( xx.x%)	xx ( xx.x%)	xx ( xx.x%)
	ANL	xx ( xx.x%)	xx ( xx.x%)	xx ( xx.x%)

[repeat for each test]

a Number of subjects with both Baseline and Day 85 results for the given treatment group.

Note: BNL=Below Normal Limit, WNL=Within Normal Limit, ANL=Above Normal Limit.

Percentages are based on the number of subjects in the Safety population with both Baseline and Day 84 results.

SOURCE: USERNAME\SPONSOR\PROJECT\JOBNAME (DATE,TIME)

Repeat Table 14.3.2.1.1 for the following:

Table 14.3.2.2.1: Summary of CBC Results by Visit (Safety Population)

**Programming note:** CBC tests include: WBC (with differentials for ANC, Neutrophils, Lymphocytes, monocytes, eosinophils, and basophils), RBC, Hemoglobin, Hematocrit, MCV, MCH, MCHC, and Platelet Count. Test names will be standardized to CDISC Controlled Terminology.

Repeat Table 14.3.2.1.2 for the following:

Table 14.3.2.2.2: Shift Table for CBC Results (Safety Population)

Repeat Table 14.3.2.1.1 for the following:

Table 14.3.2.3.1: Summary of Numeric Urinalysis Results by Visit (Safety Population)

Repeat Table 14.3.2.1.2 for the following:

Table 14.3.2.3.2: Shift Table for Numeric Urinalysis Results (Safety Population)

Table 14.3.2.3.3: Summary of Character Urinalysis Results by Visit  
(Safety Population)  
(Page 1 of y)

Test Name (Units)	BTX 1204 4% BID (N=xxx)	Vehicle BID (N=xxx)
Baseline		
n	xx	xx
xxxxxxx	xx ( xx.x%)	xx ( xx.x%)
xxxxxxx	xx ( xx.x%)	xx ( xx.x%)
xxxxxxx	xx ( xx.x%)	xx ( xx.x%)
Day 85		
n	xx	xx
xxxxxxx	xx ( xx.x%)	xx ( xx.x%)
xxxxxxx	xx ( xx.x%)	xx ( xx.x%)
xxxxxxx	xx ( xx.x%)	xx ( xx.x%)

[repeat for each test]

[figure not shown]
---

Note: Percentages are based on the number of subjects in the Safety population with a non-missing result for the given test and visit.  
SOURCE: USERNAME\SPONSOR\PROJECT\JOBNAME (DATE,TIME)

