6.3.8. Early Termination Visit

If a subject terminates the study early for reasons other than an AE, attempts will be made to complete the assessments required for the Day 85 Visit.

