7.2.2. Severity of Event

Each sign or symptom reported will be graded on a 5-point severity scale (Grade 1, 2, 3, 4 and 5).

The following definitions for rating severity will be used:

Grade 1	Mild; asymptomatic or mild symptoms; clinical or diagnostic observations only; intervention not indicated.
Grade 2	Moderate; minimal, local or noninvasive intervention indicated; limiting age-appropriate instrumental activities of daily living.*
Grade 3	Severe or medically significant but not immediately life-threatening; Hospitalisation or prolongation of hospitalisation indicated; disabling; limiting self-care activities of daily living.** Note: An experience may be severe but may not be serious, (e.g., severe headache).
Grade 4	Life-threatening consequences; urgent intervention indicated.
Grade 5	Death related to AE.

Note: A semi-colon indicates 'or' within the description of the grade.

*Instrumental activities of daily living refer to preparing meals, shopping for groceries or clothes, using the telephone, managing money, etc.

**Self-care activities of daily living refer to bathing, dressing and undressing, feeding self, using the toilet, taking medications, and not bedridden.

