#### **6.4.2 Intent-to-Treat Population**

All subjects in the randomized population who receive at least one application of study drug and have at least one post-Baseline efficacy assessment will be included in the ITT population and analyzed according to the randomized treatment group. All efficacy analyses will be presented using the ITT population.

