#### **6.4.4 Safety Population**

All subjects who receive at least one application of study drug and have at least one post-Baseline safety assessment will be included in the Safety population and analyzed according to the treatment received. All safety analyses will be performed using the Safety population.

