Table 14.3.1.2: Summary of Treatment-Emergent Adverse Event by MedDRA System Organ Class and Preferred Term (Safety Population).....	94
Table 14.3.1.3: Summary of Serious Treatment-Emergent Adverse Events by MedDRA System Organ Class and Preferred Term (Safety Population).....	95
Table 14.3.1.4: Summary of Related Treatment-Emergent Adverse Events by MedDRA System Organ Class and Preferred Term (Safety Population).....	95
Table 14.3.1.5: Summary of Severe Treatment-Emergent Adverse Events by MedDRA System Organ Class and Preferred Term (Safety Population).....	95
Table 14.3.1.6: Summary of Treatment-Emergent Adverse Events Leading to Study Discontinuation by MedDRA System Organ Class and Preferred Term (Safety Population).....	95
Table 14.3.1.7: Summary of Time to Study Discontinuation for Subjects Who Discontinue Due to Treatment-Emergent Adverse Events (ITT Population).....	96
Table 14.3.1.8: Summary of Treatment-Emergent Abuse-Related Adverse Events by MedDRA System Organ Class and Preferred Term (Safety Population).....	97
Table 14.3.2.1.1: Summary of Chemistry Results by Visit (Safety Population) .....	98
Table 14.3.2.1.2: Shift Table for Chemistry Results (Safety Population) .....	99
Table 14.3.2.2.1: Summary of CBC Results by Visit (Safety Population).....	100
Table 14.3.2.2.2: Shift Table for CBC Results (Safety Population).....	100
Table 14.3.2.3.1: Summary of Numeric Urinalysis Results by Visit (Safety Population) .....	100
Table 14.3.2.3.2: Shift Table for Numeric Urinalysis Results (Safety Population) .....	100
Table 14.3.2.3.3: Summary of Character Urinalysis Results by Visit (Safety Population).....	101

Table 14.0.1: Summary of Subject Completion/Discontinuation  
(Randomized Subjects)

	BTX 1204 4% BID (N=xxx)	Vehicle BID (N=xxx)
Completed Study		
Yes	xx ( xx.x%)	xx ( xx.x%)
No	xx ( xx.x%)	xx ( xx.x%)
Reason for Discontinuation from Study		
Adverse Event	xx ( xx.x%)	xx ( xx.x%)
Death	xx ( xx.x%)	xx ( xx.x%)
Lost to Follow-Up	xx ( xx.x%)	xx ( xx.x%)
Physician Decision	xx ( xx.x%)	xx ( xx.x%)
Pregnancy	xx ( xx.x%)	xx ( xx.x%)
Protocol Violation	xx ( xx.x%)	xx ( xx.x%)
Study Terminated by Sponsor	xx ( xx.x%)	xx ( xx.x%)
Withdrawal by Subject	xx ( xx.x%)	xx ( xx.x%)
Worsening Condition	xx ( xx.x%)	xx ( xx.x%)
Other		

SOURCE: USERNAME\SPONSOR\PROJECT\JOBNAME (DATE,TIME)

Table 14.0.2: Summary of Subjects Excluded from Analyses  
(Randomized Subjects)  
(Page 1 of 2)

	BTX 1204 4% BID (N=xxx)	Vehicle BID (N=xxx)

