Number of Subjects Included in the ITT Population	xx ( xx.x%)	xx ( xx.x%)
Number of Subjects Excluded from the ITT Population	xx ( xx.x%)	xx ( xx.x%)
Reason for Exclusion from the ITT Population		
At Least One Post-Baseline Efficacy Assessment	xx ( xx.x%)	xx ( xx.x%)
Number of Subjects Included in the mITT Population	xx ( xx.x%)	xx ( xx.x%)
Number of Subjects Excluded from the mITT Population	xx ( xx.x%)	xx ( xx.x%)
Reason for Exclusion from the mITT Population a		
Not in the ITT Population	xx ( xx.x%)	xx ( xx.x%)
No New Post-Baseline Areas of Atopic Dermatitis b	xx ( xx.x%)	xx ( xx.x%)
Number of Subjects Included in the Safety Population	xx ( xx.x%)	xx ( xx.x%)
Number of Subjects Excluded from the Safety Population	xx ( xx.x%)	xx ( xx.x%)
Reason for Exclusion from the Safety Population a		
No Evidence of Subject Dosing	xx ( xx.x%)	xx ( xx.x%)
No Post Baseline Safety Assessment	xx ( xx.x%)	xx ( xx.x%)

a Table includes primary reason (assigned in order presented in table) subject was excluded.

b The presence of new areas of atopic dermatitis were determined by post-baseline reports compared to baseline reports of BSA.

c See Listing 16.2.3 for a complete list of all other reasons for exclusion from the PP population.

Note: The ITT exclusion of not being randomized is not presented as the table is on randomized subjects.

Percentages are based on the number of randomized subjects.

SOURCE: USERNAME/SPONSOR/PROJECT/JOBNAME (DATE,TIME)

Table 14.0.2: Summary of Subjects Excluded from Analyses  
(Randomized Subjects)  
(Page 2 of 2)

	BTX 1204 4% BID (N=xxx)	Vehicle BID (N=xxx)
Number of Subjects Included in the PP Population	xx ( xx.x%)	xx ( xx.x%)
Number of Subjects Excluded from the PP Population	xx ( xx.x%)	xx ( xx.x%)
Reason for Exclusion from the PP Population a		
Violated the Inclusion/Exclusion Criteria	xx ( xx.x%)	xx ( xx.x%)
Received an Interfering Medication	xx ( xx.x%)	xx ( xx.x%)
Missed Investigator Global Assessment at Day 85	xx ( xx.x%)	xx ( xx.x%)
Missed Both Day 29 and Day 57 Visits	xx ( xx.x%)	xx ( xx.x%)
Not Compliant with Dosing Regimen	xx ( xx.x%)	xx ( xx.x%)
Day 85 Visit not within +/- 7 days Window	xx ( xx.x%)	xx ( xx.x%)
Other c	xx ( xx.x%)	xx ( xx.x%)

a Table includes primary reason (assigned in order presented in table) subject was excluded.

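### Table 14.3.1.7 puts time to AE discontinuation on ITT, against the SAP's own rule, and may miss early AE withdrawals

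*SAP*

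**What the plan says.** SAP Section 6.11.2 (Adverse Events) calls for a summary of time until study discontinuation among subjects who leave because of a TEAE. It names no population. The index in SAP Section 10 supplies one, "Subjects Who Discontinue Due to Treatment-Emergent Adverse Events (ITT Population", and the shell for Table 14.3.1.7 carries the same label.

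The general rule in SAP Section 6.4.4 has no exception: "All safety analyses will be performed using the Safety population".

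Both sets require at least one application of study drug. They differ in the second condition:

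- ITT (SAP 6.4.2): subjects must "have at least one post-Baseline efficacy assessment will be included in the ITT population", and are grouped as randomized.
- Safety (SAP 6.4.4): subjects must "have at least one post-Baseline safety assessment will be included in the Safety population", and are grouped by treatment received.

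On exit visits, Protocol Section 6.3.8 covers a subject who "terminates the study early for reasons other than an AE, attempts will be made" to complete the Day 85 assessments. The Protocol Summary, Section 4.3 and footnote b of Table 4 also deal with early exits, but make no exception for AEs.

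On severity, Protocol Section 7.2.2 states: "Each sign or symptom reported will be graded on a 5-point severity scale". Under "Maximum Severity", SAP Table 14.3.1.1 has three rows: Severe, Moderate and Mild.

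**The concern.** Safety and tolerability are part of this trial's stated objective, and how soon subjects leave because of an AE is a direct measure of tolerability. Assigning that summary to a set defined by efficacy follow-up makes inclusion depend on staying long enough to be assessed. The subjects most likely to fail that condition are those who left soonest. The report could then show one number of AE discontinuations in Table 14.3.1.6 and a smaller one in Table 14.3.1.7, with the missing subjects concentrated at short times.

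A lesser gap lies beside it. The protocol separates Grade 4 and Grade 5 from Grade 3, which it labels severe, but the SAP does not say where Grades 4 and 5 go in a three-row severity summary.

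**Working it through.** The plan gives no figure to reproduce: neither document states an expected number of AE withdrawals. The check is therefore a comparison of definitions, some date arithmetic, and an illustration on assumed times.

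**1. Is the ITT label deliberate?** Tables 14.3.1.1 to 14.3.1.6 and 14.3.1.8 are all on the Safety population; only 14.3.1.7 is not. SAP Section 8 (changes in the planned analyses) does not mention it. Nothing in the text supports an exception to Section 6.4.4.

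**2. Who can be in Safety but not in ITT?** A treated subject with a post-Baseline safety assessment and no post-Baseline efficacy assessment. If that subject leaves because of a TEAE, Table 14.3.1.6 counts the subject and Table 14.3.1.7 does not.

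**3. When can this happen?**
- First scheduled post-Baseline efficacy visit (Protocol 6.3.4): Day 15 ± 3, so 15 − 3 = Day 12 at the earliest.
- Table 14.3.1.7 measures time as discontinuation date minus first-dose date, so Day 12 is 12 − 1 = 11 days.
- Before then, ITT entry depends on an unscheduled or early-termination efficacy assessment. SAP Section 6.1.3 excludes such data from analysis before study day 9, but does not say whether they still confer ITT membership.
- A subject who misses the Day 15 visit stays at risk of omission until the Day 29 visit (29 − 3 = Day 26 at the earliest).

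**4. Direction.** Let an arm have n AE withdrawals in the Safety set. Of these, k have no efficacy assessment and mean time E; the other n − k have mean time L.

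- Safety mean = [kE + (n − k)L] / n
- ITT mean = L
- Difference (ITT − Safety) = (k/n)(L − E)

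This is zero when k = 0 and positive when E < L, which the visit schedule makes likely.

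**5. Size, on assumed times only.** Take n = 8. The k omitted subjects have the first k of the times 2, 4, 6 and 8 days. The others have the times 14, 21, 28, 35, 42, 49, 56 and 70 days, with the k shortest dropped.

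| k | Safety mean (n = 8) | ITT n | ITT mean | Difference |
|---|---|---|---|---|
| 0 | 39.4 | 8 | 39.4 | 0 |
| 1 | 37.9 | 7 | 43.0 | 5.1 |
| 2 | 35.8 | 6 | 46.7 | 10.9 |
| 3 | 33.0 | 5 | 50.4 | 17.4 |
| 4 | 29.6 | 4 | 54.2 | 24.6 |

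For k = 1: (1/8)(43.0 − 2) = 5.1 days. The table shows how the difference depends on k; it does not predict k.

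**6. Arm assignment.** A subject randomized to one arm but treated with the other would appear in different columns of Tables 14.3.1.6 and 14.3.1.7. With no dispensing errors this has no effect.

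**7. Severity.** Five protocol grades against three rows leaves 5 − 3 = 2 grades, life-threatening and fatal, without a stated place. Table 14.3.1.5 covers severe TEAEs and does not define the term. By contrast, Table 14.3.1.1 does footnote which causality categories count as related.

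**The case against.** The strongest reply is that little is at stake. Table 14.3.1.7 is one descriptive table, and SAP Section 6.11.2 rules out inference on AEs. An early AE withdrawal in the Safety set still counts in Tables 14.3.1.1, 14.3.1.2 and 14.3.1.6. Table 14.0.1, on all randomized subjects, has rows for adverse event and death. Listing 16.2.7.1.4 gives time to discontinuation by subject. The earlier Phase 1b study had no early discontinuation due to an AE (Protocol 1.2.3), so the affected group could be empty. All of this stands, and it limits the point to a correction.

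Three stronger readings are tempting, and the documents do not support them.

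- **That early AE withdrawals get no exit efficacy assessment, so ITT certainly omits them.** Section 6.3.8 limits its promise to exits not caused by an AE. The Protocol Summary says all Day 85 assessments will be completed, Section 4.3 says efforts will be made, and Table 4 footnote b says they will be performed when possible. The passages conflict, so the omission is possible but not established.
- **That life-threatening and fatal events vanish from the safety tables.** They are SAEs under Protocol Section 7.1.2. They therefore appear in the serious-TEAE rows of Table 14.3.1.1, in Table 14.3.1.3 and in Listing 16.2.7.1.3. They may also be meant to fall under Severe. Only the mapping is missing.
- **That the Safety population is itself defective because it requires a post-Baseline safety assessment.** The SAP follows Protocol Section 9.3.1 here. Table 14.0.2 has a line, "No Post Baseline Safety Assessment", that would disclose any exclusion. A wider definition is a preference, and the line does not show that anyone will be excluded.

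**Conclusion.** The contradiction is certain: Table 14.3.1.7 is on ITT and SAP Section 6.4.4 requires the Safety population. Its effect is conditional. It changes the result only if at least one treated subject withdraws for an AE with no post-Baseline efficacy assessment, or if a subject receives the wrong arm's treatment. The number of such subjects is unknown and may be zero, in which case the two versions of the table are identical. If there are any, the omission would be expected to lengthen the summarized times, given that the first scheduled efficacy visit is no earlier than Day 12. The documents do not allow an estimate of how much.

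The severity issue is a missing definition, not a loss of events. Overall this is a minor point, worth correcting because the SAP breaks its own rule and the repair is simple.

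**What to change.** 1. Relabel Table 14.3.1.7 to the Safety population in the SAP index and shell. Its n can then be checked directly against Table 14.3.1.6, with the same arm assignment.
2. Add a footnote to Tables 14.3.1.1 and 14.3.1.5, and a sentence in SAP Section 6.11.2, mapping protocol Grades 1 to 5 to Mild, Moderate and Severe. One option is Severe = Grade 3 or higher, with a note that life-threatening and fatal events are also reported as SAEs.
3. Reconcile the Protocol Summary, Section 4.3, Section 6.3.8 and Table 4 footnote b on exit assessments after an AE withdrawal. Which rule should apply is for the sponsor to settle.

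Items 1 and 2 are text and shell edits that need no new data and can be made before unblinding. Item 3 is a protocol clarification. The definition of the Safety population does not need to change.
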